****MAIN RESEARCH QUESTIONS, STUDY AIMS, SPECIFIC HYPOTHESES****

1.1 Please clearly state your overall research questions and/or study aims.

Primary Research Question:

Does combining the use of Integra®, a synthetic dermal substitute, with the application of a skin graft, known as autografting, into a one-stage procedure result in comparable outcomes to the standard two-stage procedure, so as to be a feasible, safe alternative to the standard two-stage approach?

Primary Hypothesis:

Single-stage Integra reconstruction is safe, i.e. does not result in increased infections, and effective, i.e. does not result in increased graft loss, justifying further study in small to intermediate-sized burns that could result in significantly reduced hospital stays in a specific burn population.

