****2. APPROACH****

Some questions in this section do not apply to all study designs; please mark Not Applicable as appropriate

2.1 Describe the study design (e.g., "This is a randomized controlled trial to test the effect of a guided imagery intervention on sleep quality"). Please see this List of Study Designs.

This is a prospective, descriptive, pilot case series involving patients with significant burns who are candidates for reconstruction with Integra®. Should they choose to participate in the trial, the majority of a patient's wounds would be treated in accordance with standard cares of the Regions Hospital Burn Center. However, a small area of the wound would, at the time of excision, have the smallest sheet of thin Integra® (125 cm²) placed and be immediately autografted with a 3:1 meshed split-thickness skin graft. Of note, 125 cm² represents approximately 0.7% of an average sized patient's total body surface area, so for even the smallest burns in our proposed trial, this area would represent a small portion of the patient's area of injury. The remaining injury areas would be covered with standard-thickness Integra® only. The donor graft, a 4 cm x 10 cm sheet of skin, would be meshed in a 3:1 ratio to be expanded to cover the 125 cm² sheet of thin Integra®. The patient's post-operative care would be largely unchanged, although the patient would have a donor site of 40 cm² that would be dressed and managed in the usual fashion.

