Post-operatively, the patient's care would be largely unchanged. Progress of graft "take" at the single-stage 125cm² site would be monitored regularly. Eventually, 10-14 days later, the patient would return to the operating room for eventual auto-grafting over their standard Integra®. If autograft "take" at the single-stage site was poor, the area would be regrafted. If graft "take" at the single-stage site was adequate, the area would not require additional surgery. Thus, the total number of surgeries would not be expected to change, as the patient will require two trips to the operating room regardless of trial enrollment. The 125 cm² site would be monitored daily after dressing "take-down" (typically post-operative day 5) while hospitalized and then on a standard post-operative schedule for sloughing or graft loss, infection, hematoma or underlying blood collection, seroma or underlying fluid collection, and time to 95% healed. This last variable is measured by determining the post-operative day at which 95% of the surface area of the graft is covered with epidermis. Because we are meshing the 40 cm² sheet of skin in a 3:1 fashion, the resultant graft will look like a thin fence of skin with open diamond-shaped interstices that will slowly each fill in from the peripheral surrounding skin as the graft heals. It is these interstices that give the typical meshed appearance of healed skin grafts. When 95% of the open areas have filled in, that day is determined to be the time to 95% healing. Similarly, an adjacent area of identical size, which will be treated in the standard fashion, will be monitored serially and will serve as a control. Since patients will serve as their own controls, a direct comparison between reconstruction strategies will be enabled.

Not Applicable

Eligible patients will be adults (Age 18 or older) admitted to the Regions Hospital Burn Center with thermal burns that will be reconstructed with Integra®. There is not a firm protocol in place for Integra® use – this is decided at the level of the burn attending physician on a case-by-case basis.

2.3 What is the study population of interest and what are the study inclusion/exclusion criteria?

Inclusion criteria – English-speaking adult burn patients greater than 18 years old, admitted with burn injuries eligible for Integra® reconstruction at the discretion of the burn attending physicians.

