Exclusion criteria – patients with isolated hand or face burns – these burns are treated with sheet grafts (unmeshed); the 3:1 mesh grafts would not be used on these cosmetically sensitive areas. If they have hand and/or face burns *in addition* to other areas, they will not be excluded. However, the study itself will not be performed on the hands or face. Additionally, patients unable to present to our clinic for routine follow-up due to geographic limitations or otherwise will be ineligible.

2.4 If you are not using the entire population of interest, what is the method for obtaining a subset or sample of this population?

Χ	Not Applicable

2.5 Will you need to perform "preparation for research" activities prior to consenting subjects for research?

X	No	
	Yes	
	Not	
	Applic	able

If you answered yes above, appropriate preparation for research activities prior to consenting subjects must include the following process to determine inclusion/exclusion criteria:

- 1) Study staff will work with the PI to determine the methods used in identifying potential subjects for the research. For example, this may include creating an Epic Workbench report of patients who are in the hospital and meet minimum criteria for the research.
- 2) Study staff may access medical records of all potential subjects' identified (i.e., Workbench) to determine eligibility criteria using information that already exists in the medical record. During this process, no identifiable information may be recorded and any documentation made of a potential subject's information that would disqualify them will be destroyed.

If an eligible patient is not being cared for by the PI, study staff must approach the patient's provider to determine if it is appropriate to proceed with the consent process.

- 3) If additional testing needs to be done to see whether a patient meets criteria for entry into the study, the PI or staff will need to consent the patient first.
- 4) If the preparation activity confirms a patient is a possible subject, PI/staff approaches the patient to begin the consent process.

2.6 Describe the steps in your recruitment process.

Not Applicable

Patients meeting inclusion criteria will be approached prior to their excision and Integra® placement procedure. The risks and benefits of the study will be discussed so that informed consent could be obtained.

2.7 Describe any interventions that are used in this study.

Not Applicable

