Enrolled patients will undergo a single-stage reconstruction of 125 cm² of their burn – thin Integra® will be placed with an immediate split-thickness skin graft placed at the time of the first surgery. The remainder of their injury will be treated

according to the routine standard of care – first-stage excision and Integra® placement with second-stage autografting 10-14 days later.

2.8 Provide a brief, sequential, bullet-point description of the all the data collection activities you will conduct from start to finish (e.g., chart review, patient survey, follow-up visits, data pull from the electronic medical record, etc.) and who will conduct each. Please see our Example of Data Collection Steps.

After enrollment, we will collect

- -Age, gender, %BSAB, mechanism of injury, location of burns
- -presence of burn cellulitis
- -Post-burn day of Stage 1 of reconstruction (excision, Integra® placement, and 125 cm² auto-graft)
- -location of 125cm² single-stage reconstruction site
- -percentage of graft coverage at first dressing takedown, typically post-operative day 5 and then daily
- -post-burn day of Stage 2 of reconstruction (auto-grafting over remaining Integra®, re-grafting of initial 125 cm² study area if necessary.
- -time to 95% healing of single-stage grafted area and time to 95% healing of control 125 cm² wound auto-grafted during second reconstruction procedure adjacent to the single-stage graft.
- -single-stage graft site complications (infection, hematoma, seroma, sloughing of graft)
- -adjacent (control) wound complications (infection, hematoma, seroma, sloughing of graft)

2.9 Provide a timeline for the main study activities. Please see our **Example Timeline**

October, 2016 - IRB submission

December, 2016 – February, 2016 – patient enrollment

March, 2016 - April, 2016 - Data Collection/Analysis

May, 2016 – June, 2016 – Abstract/Manuscript preparation

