2.10 Describe your plans for ensuring data security

Once a patient is enrolled they are assigned a unique identification number that is assigned to that patient for the duration of the study. The master database linking the patient name with the unique identification number is stored on one password-protected, secure computer in the Critical Care Research Center. The center is a a locked office with limited accessibility. All paper files are stored in locked cabinets at all times. Research staff are fully trained in the elements of patient privacy and confidentiality.

- 2.11. List the KEY variables that will be collected to support the study aims outlined in item 1.1. KEY variables include those used for:
 - 1) achieving the study aims (outcomes, predictors, potential confounders),
 - 2) identifying the study population (for inclusion/exclusion criteria),
 - 3) describing the study population

Please see an Example of a Completed Table and an Example Data Dictionary.

Variable Name	Data Source (patient survey, EMR, claims, registry)	Purpose (sample identification, description, grouping variable, study endpoint, predictor, covariate)	Measurement Scale (binary, continuous)
Age	EMR/Registry	Description	Continuous
Gender	EMR/Registry	Description	Binary

Percentage of Body Area Burned (%BSAB)	EMR/registry	Description	Continuous
Burn Location(s)	EMR	Description	Descriptive
Presence of Burn Cellulitis	EMR	Confounder	Binary
Post-Burn Day of Stage 1 (Tangential Excision/Integra® Placement with 125 cm² of auto-grafting)	EMR	Covariate	Continuous
Location auto-grafted	EMR	Description	Descriptive
Complications of Integra®	EMR	Covariate	Descriptive
Time to 95% healing of single-stage skin graft	EMR	Study Endpoint	Continuous
Complications of Stage 1 Auto-graft (infection, hematoma, seroma, sloughing)	EMR	Study Endpoint	Descriptive
Post-Burn Day of Stage 2 (auto-grafting remaining Integra areas)	EMR	Covariate	Continuous
Location of control autograft	EMR	Description	Descriptive
Time to 95% healing of control skin graft	EMR	Study Endpoint	Continuous
Complications of control skin graft (infection, hematoma, seroma, sloughing)	EMR	Study Endpoint	Descriptive

2.12 Provide operational definitions of any variables listed above that aren't adequately described by the variable name above, and provide a brief background of any validated measurement scales listed above.

n/a

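### No rule says which of two adjacent 125 cm² areas gets the single-stage graft, or when the control is fixed, so the Aim 2 comparison is open to site-selection bias

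*Combined protocol and SAP*

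**What the plan says.** Section 2.1 describes the single-stage site only as follows: "a small area of the wound would, at the time of excision, have the smallest sheet of thin Integra" placed, with an immediate graft. For everything else, "The remaining injury areas would be covered with standard-thickness Integra® only". The control is described thus: "an adjacent area of identical size, which will be treated in the standard fashion, will be monitored serially and will serve as a control". From this the section concludes that "a direct comparison between reconstruction strategies will be enabled".

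Section 2.3 gives the only siting rule, and it is an exclusion: "the study itself will not be performed on the hands or face". Section 2.8 says when the control is grafted ("auto-grafted during second reconstruction procedure adjacent to the single-stage graft") but not when it is chosen. Section 2.11 lists "Location of control autograft" and the single-stage location as descriptive variables, and section 2.12, which asks for operational definitions, is answered as not applicable.

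Section 3.1 makes Aim 2 a comparison of the two areas, using t-tests for healing time and chi-square tests for complications. The hypothesis in section 1.1 is that the single-stage method "does not result in increased infections, and effective, i.e. does not result in increased graft loss". The limitations in section 3.9 cover the number of patients and the size of the grafted area, not site choice.

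**The concern.** Using patients as their own controls removes differences between patients. It does not remove differences between two areas of one wound, such as depth, closeness to the edge or quality of the bed. If the choice between the areas follows such differences, the estimated treatment effect contains them.

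Two gaps leave this open. The first is that nothing says who or what decides which area is treated in one stage. The second is that the control has no visible boundary: it receives the same standard Integra and the same second-stage graft as the rest of the wound, so it exists only once someone draws it. Single-stage take can be seen from about post-operative day 5, and the second operation comes at 10 to 14 days. As written, the control could be drawn after the single-stage result is known.

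Infection and graft loss carry the safety and effectiveness hypothesis, and section 3.9 presents the result as a step towards a multi-institutional study. Aim 1, which only describes the single-stage site, needs no allocation and is not affected in this way.

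**Working it through.** **What the plan gives.** Section 3.2 plans 10 patients, hence 10 pairs of areas. Section 3.4 justifies this by feasibility, and there is no power or precision figure to reproduce. No SD, alpha, margin or complication rate is stated, so everything below rests on assumptions: no true treatment effect and a two-sided 5% level.

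**Healing time.** Write the within-patient difference as D = ±|S| + E, scaled so that its mean square is 1. S is the normally distributed site difference visible to the person choosing, and f is its share of the variance. One treatment receives the better area with probability p. Then

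bias = (2p − 1) × √(2f/π).

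For example, p = 0.75 and f = 0.50 give 0.5 × √(1/π) = 0.5 × 0.564 = 0.282.

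| Better area to one treatment | f = 0.10 | f = 0.25 | f = 0.50 | Paired t-test rejections, 10 pairs |
|---|---|---|---|---|
| 50% | 0 | 0 | 0 | 5% |
| 60% | 0.050 | 0.080 | 0.113 | 5.2%, 5.7%, 6.5% |
| 75% | 0.126 | 0.199 | 0.282 | 6.5%, 9.2%, 14.1% |

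The limiting case is p = 1, where the area judged better always goes to the same treatment. If that judgement correlates 0.3, 0.5 or 0.8 with the true difference (f is the square of this), the bias is 0.24, 0.40 or 0.64 SD. Paired rejections are then about 11%, 23% and 65%. The size therefore depends heavily on how strong the selection is.

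**Against chance.** The 95% half-width is t(0.975, n − 1)/√n, which is 0.715 SD for n = 10, 0.284 for n = 50 and 0.198 for n = 100. At 10 pairs, mild selection is small beside sampling error. At 100 pairs, a bias of 0.28 SD exceeds the half-width.

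**If the t-test is unpaired.** Section 3.1 does not say that it is paired. With a within-patient correlation of 0.5, the unpaired test rejects about 0.9% of the time with no shift, 1.2% at 0.1 SD, 3.1% at 0.25 SD and 11.9% at 0.5 SD. The bias in the estimate is the same. The harm that holds under either test is the biased estimate, not an inflated test.

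**Complications.** Bias in the risk difference = (2p − 1) × (risk at worse area − risk at better area). Outcomes in the two areas are taken as independent, and the chi-square test as uncorrected.

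| Assumed risks, better/worse | Bias at 60% | Bias at 75% | Chi-square rejections, 50% → 75% |
|---|---|---|---|
| 10% / 20% | 2 points | 5 points | 2.2% → 2.8% |
| 10% / 30% | 4 points | 10 points | 3.6% → 6.1% |

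The test hardly moves, but the observed pattern does. At 10%/30% and 75% selection, the favoured treatment shows fewer complications in 61% of such studies, against 39% with no selection. If the single-stage graft were the favoured one, a true 20-point excess would appear on average as 20 − 0.5 × 20 = 10 points.

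**The case against.** The strongest reply is that the plan calls itself a descriptive pilot case series and promises no randomised comparison. It requires the control to be adjacent and of equal size, treats the single-stage area at excision, records both locations and plans photographs. Nothing says that anyone steers a treatment to the better area. When the control is grafted, its own graft outcome does not yet exist, so seeing the single-stage result does not by itself reveal which neighbouring area will heal faster. All the magnitudes are assumed, and at 10 pairs they lie inside the confidence interval.

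Much of this stands. Adjacency and equal size narrow the choice, late designation is a possibility rather than a finding, and the figures show a range, not an expectation. The 61% and 39% in particular depend on treating the two areas as independent; shared patient-level risk would change both. A successor study need not site grafts in the same way.

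It does not close the gap. A descriptive difference is biased by site choice just as a tested one is, and the plan both tests the difference and calls the comparison direct. Recording locations afterwards does not show why they were chosen. By the second operation the state of the standard-Integra bed is visible, and that could guide where the control is drawn.

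**Conclusion.** The concern holds. In the text available (some pages were removed before review) there is no rule for choosing between the two areas and no time at which the control is fixed, so the Aim 2 estimates may be biased in either direction. Under the assumptions shown, 60% to 75% selection gives 0.05 to 0.28 SD for healing time and 2 to 10 percentage points for a complication. In 10 patients this is mostly smaller than chance error. It matters because the plan leans on the comparison, more patients sited the same way would not dilute the bias, and prevention is cheap. The change should be made, with medium confidence in how much it matters. Aim 1 can stand as planned.

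**What to change.** **Preferred.** At Stage 1, after excision, mark, photograph and record two adjacent 125 cm² areas, outside hand and face, that the surgeon judges equally suitable. Then open a sealed envelope prepared in advance that assigns one to single-stage and the other to control. Describe site allocation as randomised within patient. This removes site-selection bias in expectation and prevents the control from being chosen after the single-stage result is seen.

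**Minimum, keeping the case-series design.** Mark and record both areas at Stage 1 under a stated siting rule, and list site choice as a limitation in section 3.9. This settles the timing. A rule that asks for comparable areas would also narrow visible differences, but discretion over which area gets which treatment remains.

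**Cost.** The minimum needs a short amendment and a marked photograph. Wound and graft photographs are already planned (section 8.10), and the control already implies 2 × 125 = 250 cm² of adjacent wound. Randomising adds a 10-patient sequence, someone to hold the envelopes, opening one in the operating room, and rewording the design label. The surgeon must accept either area. The sample size does not change.

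**What remains.** Chance imbalance is still possible with 10 patients: one treatment receives 8 or more of the better areas with probability 0.11, and 7 or more with probability 0.34. Neither version addresses thin versus standard Integra, the different grafting days or unblinded assessment.

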****1. BACKGROUND & SIGNIFICANCE****

1.2 What is the specific knowledge gap that the project intends to fill? Include a brief review of past research in this area, numbering your citations to relevant literature as well as including them in the reference section #9.1.

Integra®, a synthetic dermal substitute, has been utilized in burn care for decades.¹ Composed of a porous collagen-chondroitin 6-sulfate fibrillary mat covered with a thin sheet of silastic, it serves to cover wound beds of freshly excised burns and allow for the infiltration of fibroblasts, capillaries, and macrophages, essentially creating a "neodermis" while also acting as a barrier against infection and a blockade against heat and moisture loss.¹ Typically, 10-14 days after Integra® placement, a patient returns to the operating room, the top silastic layer of the Integra® is removed, and an autograft — a split-thickness skin graft harvested from the patient — is applied directly on top of the incorporated Integra®. The result is regarded to be a cosmetically and functionally superior result to that which would have been obtained had the wound bed itself been autografted at the time of excision, as opposed to being covered by Integra® and autografted during a second operation.

Advantages of Integra® use are several.

- There are cosmetic advantages and functional advantages to the end result when compared with grafting alone.^{2,3}
- Integra® provides a temporary infection and moisture loss barrier until the definitive coverage with the split-thickness skin graft. This divides the overall reconstruction, and, therefore, the associated physiologic insult into two stages. It should be noted that this advantage did not start with the invention of Integra® homograft and allograft (cadaver) coverage provided temporary coverage prior to the advent of Integra®.
- The neodermis allows for definitive coverage to be done with a thinner split-thickness skin graft than would otherwise be utilized to cover an Integra®-free wound bed. This allows for faster donor site healing with decreased scarring and pain. Additionally, in the setting of larger burns, the faster donor site healing means a shorter time until these donor sites can be re-harvested to cover additional burned sites.

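### The donor wound made at the first operation is not observed in the data list, the endpoint table or the analysis, so an infection there would not enter the safety result

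*Combined protocol and SAP*

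**What the plan says.** Section 2.1 has a 4 cm x 10 cm sheet of skin harvested at the first operation, meshed and laid over the thin Integra. It notes the consequence: "the patient would have a donor site of 40 cm² that would be dressed and managed in the usual fashion". It then sets out post-operative observation of the study site ("The 125 cm² site would be monitored daily after dressing" take-down) and serial observation of an adjacent control area of the same size. If take "at the single-stage site was poor, the area would be regrafted" at the second operation.

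The items to be collected follow that pattern. Section 2.8 lists "single-stage graft site complications (infection, hematoma, seroma, sloughing of graft") and "adjacent (control) wound complications (infection, hematoma, seroma, sloughing of graft"), with time to 95% healing for each of the two areas. Section 2.11 labels four rows as study endpoints: healing time and complications for the single-stage graft, for example "Complications of Stage 1 Auto-graft (infection, hematoma, seroma, sloughing"), and the same pair for the control graft. Section 3.1 describes and compares these two grafts.

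The hypothesis in 1.1 reads: "Single-stage Integra reconstruction is safe, i.e. does not result in increased infections". It does not limit those infections to the graft bed. Section 3.9 makes a finding of safety and effectiveness the basis for a multi-institutional study.

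**The concern.** The donor wound is the one change in post-operative care that section 2.1 itself singles out, yet the plan never turns it into an observation. Section 1.2 shows that the authors regard donor-site outcome as clinically relevant: among the advantages of grafting over a neodermis with a thinner graft, it says "This allows for faster donor site healing with decreased scarring and pain".

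What is at stake is the reach of the word 'safe'. Under the plan as written, a patient whose Stage 1 donor site became infected or healed slowly would contribute nothing adverse to the safety summary. The report could then state that infections did not increase after looking at only one of the two wounds that the single-stage procedure involves. A follow-on study that grafts larger areas at the first operation would need larger early harvests, and this pilot would give it no donor-site description to plan from.

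**Working it through.** **1. The plan's own figure.** The sheet is 4 cm x 10 cm (2.1), so the donor area is 4 x 10 = 40 cm², as stated.

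**2. Its size in context.**
- Relative to the study area: 40 / 125 = 32%.
- Relative to body surface: section 2.1 equates 125 cm² with about 0.7%, so 0.32 x 0.7% = about 0.22%.
- Over the planned 10 patients (3.2): 10 x 40 = 400 cm² harvested at the first operation.

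**3. Where a donor-site item could appear.**

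| Place | What it covers | Donor-site items |
|---|---|---|
| 2.1, monitoring | study site and adjacent control area | 0 |
| 2.8, collection list | healing and complications of those two areas | 0 |
| 2.11, study endpoints | four rows, two per graft | 0 of 4 |
| 3.1, analysis | the same two grafts | 0 |

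The remaining row in 2.11 on complications, a covariate, concerns the Integra and not the donor site. Section 8.10 ticks procedures, provider notes, and photographs of wounds and grafts. These could capture a donor-site problem by chance, but no variable, schedule or analysis uses them for that purpose.

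**4. Shifted or added?** The control area also needs an autograft at Stage 2, and so a donor wound of its own. Without the trial, the study area would have been grafted then too.
- Adequate take: one harvest for the study area, made 10-14 days earlier. The change is in timing and possibly in graft thickness, which is not recorded.
- Poor take and regraft: a second harvest for the same area. Extra area = (number regrafted) x (area harvested per regraft).

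The documents give no regraft rate. For an assumed 0 to 3 regrafts in 10, each of a full 40 cm², the extra is 0 to 3 x 40 = 120 cm². Zero belongs in the range: none of the six preliminary cases in 1.3 was rated poor. Six cases are weak evidence, however. The exact two-sided 95% upper limit for 0 of 6 is 1 - 0.025^(1/6) = 45.9%, and those were chronic wounds, not burns.

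**5. What donor-site data in 10 patients could show.**
- Zero events in 10: the exact two-sided 95% upper limit is 1 - 0.025^(1/10) = 30.8%. With 9 evaluable patients, 1 - 0.025^(1/9) = 33.6%.
- Chance of at least one event in 10, 1 - (1 - p)^10, at assumed true rates: 40% (p = 5%), 65% (10%), 89% (20%), 97% (30%). The documents state no donor-site event rate.

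So a common problem would probably be seen if it were recorded, and a rare one could not be excluded.

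**The case against.** The strongest reply is that this is a 10-patient descriptive pilot, that the donor wound is small beside the patient's burn, that its care is standard, and that an upper limit near 31% proves little. All of that is true. It limits what can be concluded, but it does not justify an unrestricted statement about infections that leaves this wound out.

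Three stronger readings are tempting and should not be drawn.

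- **That the trial adds 400 cm² of donor wound.** It does not, in general. The study area would have needed skin at Stage 2 anyway, so the harvest is mainly moved earlier. Even a regraft falls at an operation where skin is already being taken, and need not use a full 40 cm².
- **That section 1.2 shows the single-stage method forfeits a donor-site benefit of the two-stage method.** Its comparison is with a wound bed that has no Integra, and the single-stage site does have Integra beneath the graft. The documents give no graft thickness for either approach, so any loss is conjecture. The section shows only that donor-site outcome matters to the authors.
- **That regrafting goes unrecorded.** Section 2.8 mentions regrafting of the study area, if needed, in its Stage 2 item, and graft coverage is collected daily. What is missing is a clear regraft variable and the area harvested for it.

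Section 4 of the form is not in the text available for this point, so relevant wording there cannot be ruled out. The list, table and analysis named above can be read.

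**Conclusion.** The omission stands. The Stage 1 donor site is absent from 2.8, 2.11 and 3.1, so a donor-site infection or delayed donor healing would not enter the planned safety result, although 1.1 defines safety through infections without restricting the site. It concerns all 10 patients, with 40 cm² each.

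The consequence is an incomplete safety statement. The comparison of the two grafts is unaffected, and nothing here suggests that the donor wound would go without care. The extra burden, as distinct from earlier timing, arises only with regrafting: 0 to 120 cm² in total under the assumed 0 to 3 full-size regrafts. The conclusion rests on the plan being followed as written, with no donor-site safety item elsewhere in the protocol. It is a cheap improvement, worth making before enrolment.

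**What to change.** - **2.8 and 2.11:** for the Stage 1 donor site, add infection, post-operative day healed, harvested area and graft thickness. Record the same items for the Stage 2 donor site or sites at patient level; no part of that harvest has to be assigned to the control area. Section 2.12, now answered as not applicable, should say how donor-site infection and healing are judged.
- **Regrafting:** add a yes/no variable for the study site and, where yes, the extra area harvested.
- **3.1:** report these items descriptively beside the graft-site infections, as counts with exact confidence intervals. Stage 2 harvests serve all remaining Integra, so the two operations' donor sites differ in size and should not be tested against each other.
- **1.1 and 3.9:** state that the safety conclusion covers graft and donor sites, and that the donor-site part is descriptive.

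Cost: slightly more data entry in 10 patients, at operation and at checks already planned. Treatment, schedule and sample size do not change. The limit is precision: 0 of 10 would still be compatible with a donor-site event rate of up to about 31%.
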